# ECG

The following classes will be derived for **QTCF** : <= 450,] 450; 480],] 480; 500] and > 500

# 4.1.6 Miscellaneous

- All the summarized tables mentioned in this SAP will be provided as RTF/HTML or WinWord compatible format (and not as text format). This allows direct insertion of these tables unchanged in the Clinical Study Report.

-Unless otherwise specified, the significance test will be conducted at a two-sided significance level of 0.05

-A third party statistician will independently review the Statistical Analysis Report before disclosing the results.

# 4.2 Sample size calculation

(ICH E3; 9.7.2. ICH E9; 3.5)

The initial protocol was based in assuming a Pearson correlation coefficient of R=0.5 between prebaseline and final values of PDSS, two pre-baseline measurements [(V1+V2)/2] and two post-baseline measurements [(V6+V7)/2]. A standardized mean difference of at least 0.5 (considered as the minimum clinically significant difference) will be detected at a two-sided 0.05 confidence level with a power of at least 0.8, when the sample size/group is at least 20 and 40 patients for control and tested drug groups, respectively.

At a later stage, UNS measuring EDS and cataplexy was used as the primary outcome instead of the PDSS. As UNS was expected with a residual variability larger than PDSS, the initial power of .75 judged as too small, a recalculation of the sample size was performed on a standardized mean difference of 0.5 on the UNS (considered as the minimum clinically significant difference), a ratio 1:2, and a correlation R=0.4. Under these assumptions, and ANCOVA test at 0.05 two-sided confidence level, the probability of a significant effect will be found with a power of 0.85 when the sample size exceeds 36+72 patients for control and tested drug groups, respectively, thus a total of 108 patients.

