	of the sample size. At least 96 patients (64 patients being administrated pitolisant, and 32 patients receiving placebo) should be needed for a power of at least 0.75, given the observed values of SD and baseline correlation.
	A new sample size was calculated further the change of the main endpoint and adjustment of the corresponding variability (SD and baseline correlation):
	A difference of at least UNS=3 between the studied treatment and placebo with the observed values of SD and baseline correlation will be detected as significant with a power of 85%, once the sample size is at least 36+72 patients for control and tested drug groups, respectively, thus a total of 108 patients.
Study duration for	Inclusion period 4 weeks (including 2-week baseline period). Followed by, Double-blind period, treated by pitolisant or placebo for 8 weeks,
participants	Followed by, Single blind wash-out period, treated by placebo for 1 week and then Followed by a prolonged open-label period depending on patient wish.
	1) Male and female children from 6 to less than 18 years of age (until V8) suffering from narcolepsy with or without cataplexy - meeting the International Classification of Sleep Disorders (ICSD-3) criteria (narcolepsy type 1 and 2). Diagnosis confirmed with polysomnography and Multiple Sleep Latency Test for patients without cataplexy (if these examinations were not performed within the last 12 months)
	 2) PDSS score ≥ 15 during baseline period (V1+V2) / 2. 3) Patients should be free of non-authorized medication, in particular psychostimulant treatments as from the screening visit (V0) onwards.
Main inclusion criteria	4) Parents – and patients old enough to understand who have expressed a willingness to participate in the study, who have signed and dated the informed consent form prior to beginning protocol required procedures.
	5) In the opinion of the investigator, the patient must have adequate support to comply with the entire study requirements as described in the protocol (e.g., transportation to and from trial site, self rating scales and diaries completion, drug compliance, scheduled visits, tests).
	6) Female pubescent patients shall use a birth control method, judged efficient by the investigator, throughout the study and during the month following treatment discontinuation.
	7) Patients should benefit from appropriate healthy insurance system (only applicable where mandatory e.g. in France).

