Statistical Analysis	The primary selection will be the Full Analysis Set (FAS), defined as all the randomized patients irrespective of their outcome, this analysis with the best conformity with Intent To Treat principle.

BIOPROJET Version 3.0 Protocol P11-06/ BF2.649 September 30th, 2020 EudraCT number: 2013-001506-29

The main endpoint is the UNS measuring the quantity and intensity of symptoms of narcolepsy in particular of EDS and cataplexies.

Metric properties of this scale are summarized as follows: Total scores range from 0 to 44 with higher scores denoting greater narcoleptic tendencies.

The significance of the active tested drug compared with placebo on the change of UNS will be assessed by Analysis of Covariance on Final UNS estimate (the summary mean of the two Final UNS measures V6 and V7) adjusted for baseline (summary mean of the two pre-treatment UNS values V1 and V2). ANCOVA will be conducted with a Mixed Linear Model taking into account centre heterogeneity.

A standardized mean difference of at least 0.5 on the UNS (considered as the minimum clinically significant difference) will be detected at a two-sided 0.05 confidence level with a type 2 risk of 0.15 (power \geq 0.85), assuming a baseline-final correlation R=0.4, and a sample size ratio 1:2 when the sample size/group is at least 36+72 patients for control and tested drug groups, respectively, thus a total of 108 patients.

For patients terminating the trial before completion, the final value will be calculated as the mean of the two last known values (baseline if needed).

The independent Data Safety Monitoring Board (DSMB) will regularly follow the progress of the clinical trial, monitor safety data and critical efficacy variables and be consulted concerning the opportunity of modifying the sample size (see next point), or terminate a trial for futility (see next point).

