7.4. STATISTICAL INFERENCE

The significance of the active tested drug compared with placebo on the change of UNS will

be assessed by Analysis of Covariance on Final UNS estimate (the summary mean of the two

Final UNS measures V6 and V7) adjusted for baseline (summary mean of the two pre-treatment

UNS values V1 and V2). ANCOVA will be conducted with a Mixed Linear Model taking into

account centre heterogeneity.

SAMPLE SIZE DETERMINATION

By assuming a Pearson correlation coefficient of R=0.5 between pre-baseline and final values

of PDSS, two pre-baseline measurements [(V1+V2)/2] and two post-baseline measurements

[(V6+ V7)/2], a standardized mean difference of at least 0.5 (considered as the minimum

clinically significant difference) will be detected at a two-sided 0.05 confidence level with a

power of at least 0.8, when the sample size/group is at least 20 and 40 patients for control and

tested drug groups, respectively.

In the last sample size calculation as detailed in section 7.7.2, a recruitment of 96 patients was

decided, based on the following assumptions: a standardized mean difference of at least 0.5

(considered as the minimum clinically significant difference) will be detected at a two-sided

0.05 confidence level with a power \geq 0.75. Since then, the main endpoint becomes the UNS

measuring EDS and cataplexy instead of the PDSS. The validation of UNS provided good

metric properties, but a residual variability slightly larger than PDSS. The power 0.75 was also

considered risky and increased to 0.85.

Further to those changes, a recalculation of the sample size was performed on a standardized

mean difference of 0.5 on the UNS (considered as the minimum clinically significant

difference), a ratio 1:2, and a correlation R=0.4. Under these assumptions, and ANCOVA test

at 0.05 two-sided confidence level, the probability of a significant effect will be found with a

power of 0.85 when the sample size exceeds 36+72 patients for control and tested drug groups,

respectively, thus a total of 108 patients.

HANDLING OF MISSING DATA

For patients terminating the trial before completion, the final value will be calculated as the

Confidential

93

EudraCT number: 2013-001506-29

mean of the two last known values (baseline if needed).

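### The stated power of 0.85 at 36+72 does not follow from the stated inputs, which give about 0.75 to 0.76 at two-sided 0.05

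*SAP*

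**What the plan says.** SAP 4.2 states that "a recalculation of the sample size was performed on a standardized mean difference of 0.5 on the UNS", with allocation 1:2, R=0.4 and a two-sided 0.05 ANCOVA, and concludes that "the probability of a significant effect will be found with a power of 0.85 when the sample size exceeds 36+72 patients". The claim appears three more times in the protocol:

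- Synopsis, Sample Size: a difference of at least 3 UNS points "will be detected as significant with a power of 85%, once the sample size is at least 36+72 patients".
- Synopsis, Statistical Analysis: the SMD of 0.5 is to be detected "at a two-sided 0.05 confidence level with a type 2 risk of 0.15".
- Section 7, sample size determination: "power of 0.85 when the sample size exceeds 36+72 patients for control and tested drug groups".

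The synopsis also defines the variables analysed: "Final UNS estimate (the summary mean of the two Final UNS measures V6 and V7) adjusted for baseline (summary mean of the two pre-treatment". Outcome and covariate are thus both two-visit means (V6/V7 and V1/V2), and R=0.4 is called the baseline-final correlation. SAP 4.1.6 says that, unless otherwise specified, "the significance test will be conducted at a two-sided significance level of 0.05".

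Protocol section 7 gives the reason for the last recalculation: the earlier power of 0.75 was "considered risky and increased to 0.85".

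**The concern.** The plan prints every input that a standard ANCOVA power calculation needs, and that calculation falls about 9 percentage points short of the stated power. The recalculation was meant to move the trial away from a power of 0.75. On the printed inputs it stays there.

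The UNS is also first in the fixed sequence of SAP 4.1.3.2. A missed UNS result stops formal testing of PDSS, UNS-CTP, WRC and MWT. Anyone interpreting a non-significant UNS result would rely on a type 2 risk of 0.15 that the inputs do not support.

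**Working it through.** **Inputs.** SMD d=0.5, R=0.4, n=36 (placebo) and 72 (pitolisant), two-sided 0.05 (SAP 4.2; protocol synopsis and section 7). No dropout allowance is stated, so none is applied.

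**Direct reading: d and R refer to the two-visit means.**

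- Residual variance factor: 1 − R² = 1 − 0.16 = 0.84.
- Size term: √(36×72/108) = √24 = 4.899.
- Noncentrality: 0.5/√0.84 × 4.899 = 2.673.
- Power, normal approximation: Φ(2.673 − 1.960) = 0.762.
- Power, noncentral t with 105 df: 0.754.
- 40,000 simulated ANCOVAs with a random baseline: 0.747 (Monte Carlo SE 0.002).

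**What would give 0.85 on this reading.**

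| Change to one input | Normal | Noncentral t |
|---|---|---|
| One-sided 0.05, 36+72 | 0.848 | 0.844 |
| 45+90 = 135 patients | 0.848 | 0.843 |
| 46+92 = 138 patients | 0.856 | 0.851 |
| SMD needed at 36+72 | 0.561 | 0.566 |
| R needed at 36+72 | 0.576 | 0.586 |

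If 3 UNS points equal 0.5 SD, the implied SD is 6, and an SMD of 0.561 to 0.566 is about 3.4 points. A one-sided test nearly reproduces 0.85, so it is a possible source of the figure, but every statement of the test is two-sided.

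**Single-visit reading: d and R refer to one visit.** Let W be the correlation between paired visits (V1 with V2, V6 with V7). The variance factor becomes (1+W)/2 − R²/[(1+W)/2]. At 36+72 with R=0.4 (normal approximation):

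| W | 0.4 | 0.5 | 0.6 | 0.7 | 0.71 | 0.8 | 1.0 |
|---|---|---|---|---|---|---|---|
| Power | 0.946 | 0.917 | 0.885 | 0.853 | 0.850 | 0.822 | 0.762 |

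So 0.85 requires W of about 0.71. Neither document gives W.

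**Cross-check on the original step (20+40, R=0.5, stated power at least 0.8).**

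- Direct reading: Φ(0.5/√0.75 × √(20×40/60) − 1.960) = 0.559.
- Single-visit reading: 0.807 with W=0.5, but 0.682 with W=0.71.

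W=0.5 fits the original step but gives 0.917 at 36+72. W=0.71 fits 36+72 but gives 0.682 at 20+40. No single W reproduces both stated figures.

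**Cross-check on the step from 96 to 108.** Protocol section 7 says 96 patients give power of at least 0.75 at SMD 0.5. This check needs neither W nor a particular formula, only an unchanged standardized effect and residual variance.

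- Going from 0.75 to 0.85 multiplies the sample size by [(1.960+1.036)/(1.960+0.674)]² = 1.29, so 96 becomes about 124.
- The plan adds 108/96 − 1 = 12.5%. If power is 0.75 at 96, then at 108 it is Φ(2.634×√1.125 − 1.960), about 0.80.

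Section 7 also says the UNS has slightly larger residual variability than the PDSS, which would lower this further.

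**The case against.** The strongest reply is that 0.75 to 0.76 is the bottom of a range rather than the established power. The original step lists two measurements before and two after baseline among its inputs. Its stated 0.8 is reproduced by the single-visit formula with all correlations at 0.5 (0.807), not by the direct reading (0.559). The same convention with all correlations at 0.4 gives 0.946 at 36+72, so 0.85 could even be an understatement. The two steps use different scales. PDSS asks about the past week, while most UNS items are graded by frequency categories running up to lifetime, so a higher paired-visit correlation for the UNS is plausible. There is also a mixed route: R on the means with the SMD in single-visit SD units gives 0.848 at W=0.6. Finally, the synopsis ties the 85% to an observed SD that is not printed. If that SD were 5.3 (an assumption), 3 points would give 0.857.

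Part of this stands. The single-visit reading cannot be excluded, and the figure of about 0.75 is conditional on the direct reading. But the single-visit and mixed routes need a paired-visit correlation that the documents do not state, and the SD of 5.3 contradicts the printed SMD of 0.5. The synopsis defines baseline and final as two-visit means and then gives a baseline-final correlation, so the direct reading is the natural one. The small increase from 96 to 108 remains unexplained on any single basis.

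**Conclusion.** The concern holds. On the printed inputs, with the SMD and R taken on the two-visit means, complete data and a two-sided 0.05 test, power at 36+72 is 0.754 to 0.762 (simulated 0.747) against 0.85 stated. The type 2 risk is about 0.24 to 0.25 against 0.15. That is essentially the level the protocol called risky.

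If single-visit quantities were meant, power lies between 0.76 and 0.95 for W from 1 to 0.4, and 0.85 is then one undocumented point in that range. Either way, the stated inputs do not deliver the stated power. This is an error in a planning figure: the estimator, type I error and p-value are not affected.

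**What to change.** Keep N=108 and correct the statement in four places: the protocol synopsis (Sample Size and Statistical Analysis), the sample size determination in protocol section 7, and SAP 4.2.

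- If the SMD and R are on the two-visit means, state that power is about 0.75 at two-sided 0.05 for SMD 0.5 and R=0.4, and that power 0.85 corresponds to an SMD of about 0.56 to 0.57.
- If single-visit quantities were intended, state the SD basis, what R refers to, the correlation between paired visits and the formula, and give the power they yield.

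The cost is wording only. The stated power becomes less favourable, or the missing correlation has to be disclosed. No extra patients are needed, and neither the conduct nor the analysis changes.

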# 4.3 Analysis populations and subgroups

# Screened Set (ScS):

All patients with an Informed consent form signed.

# Randomised Set (RS):

All randomized patients.

# Full Analysis Set (FAS):

In accordance with the intention-to-treat principle and Section 5.2.1 of the ICH E9 guideline, all randomised patients who received at least one dose of IMP and who have at least one baseline value of UNS (primary efficacy criterion).

# Per Protocol Set (PPS):

Consists of all patients in the FAS without any major protocol deviation and having one total score UNS value at V6 or V7.

A protocol deviation is major when it has a possible effect on the outcome. As to whether a deviation is major or minor is fixed during the Blind Review Meeting.

The Per protocol analysis will be conducted at the condition that its sample size should be less than 90% of the FAS.

# Safety Set (SAF):

All patients who receiving at least one treatment dose.

4 subgroups will be used in some analyses, according to:

- Age at baseline ([6-11], [12-18[)
- Sex
- BMI at baseline (underweight , normal, overweight and obese)
- Type of narcolepsy (Type 1 or Type 2)

# 4.4 Protocol deviations

PDs will be defined as early as possible during the study conduct.

All PDs will be carefully identified through eCRF data before the BDRMs. During the BDRMs held before database lock (DBL), each PD will be classified as leading to exclusion from the PP population ("major") or not leading to exclusion from the PP population ("minor").

All PDs related to study inclusion or non-inclusion criteria, conduct of the trial, patient management or patient assessment will be described, such as:

- Violation of inclusion criteria
- Violation of exclusion criteria
- Intake of non-allowed concomitant medications
- Randomisation error
- Lack of compliance
- Etc.

Additionally, the PDs that could not be identified through eCRF data will also be reviewed during the BDRMs. This listing will be based on the PD forms completed by the study team. Any "major" PD or information needed to conduct the statistical analyses will be extracted from the listing and imported in the database.

# 4.5 Statistical analyses

Details concerning definitions about derived parameters are provided in section 4.1.5.

# 4.5.1 Disposition and Baseline characteristics

Disposition of patients and baseline characteristics will be described by randomised treatment group, to assess their comparability, and overall (treatment groups pooled).

# 4.5.1.1 Patients disposition

Disposition of patients, including reasons for withdrawal, will be summarized during the study by randomised treatment, overall and by center, in the RS and in the FAS.

If necessary a listing of non-included randomised patients will be provided.

# 4.5.1.2 Protocol deviations

Protocol deviations at inclusion or after inclusion on V2-V8 period, will be described in the RS, by category of important deviations (based on ICH E3 guideline and ICH E3 Q&A).

# 4.5.1.3 Demographic data and other baseline characteristics

Demographic data and other baseline characteristics such as age, sex, contraception, narcolepsy history, ECG, vital signs, Polysomnography and Multiple Sleep Latency Test, Clinical Global Impression of baseline Severity (CGI-S) and baseline value of endpoints characteristics will be described. As the populations RS and FAS are identical, only description in the RS will be done. All previous treatments will be described.

# 4.5.2 Treatments of patients

Details concerning definitions on extent of exposure, treatment compliance and concomitant treatments are provided in section 4.1.5.

# 4.5.2.1 Extent of exposure and treatment compliance

Extent of exposure (Study duration (days) and treatment duration (days)) and treatment compliance (%) will be described in the FAS and the SS.

The treatment duration will be described on the period V2-V7.

## 4.5.2.2 Concomitant treatments

All concomitant treatments (specific and non-specific) taken at inclusion and during the treatment period (over the V2-V7 period) will be described in the RS, by ATC code.

A listing will be provided for every patient documenting the existing concomitant medication with date of start and end of treatment.

## 4.5.3 Efficacy analysis

All efficacy analyses will be performed by randomised treatment group in the FAS and in the PPS. For inferential analyses involving several results according to the imputation method (MAR, MNAR and observed cases), if there isn't any missing data in the Per Protocol Set, consequently only results with observed cases will be compute.

## 4.5.3.1 Primary endpoints

The Ullanlinna Narcolepsy Scale (UNS) is an 11-item scale measuring the intensity and frequency of symptoms of narcolepsy. The first four items address typical manifestations of cataplexy occurring in situation as laughing, feeling glad or angry or any exciting situation. The 7 other items measure the sleep latency and the propensity to fall asleep in various situations. The total severity score varies from 0 to 44.

## **Definition:**

The primary efficacy endpoint is defined as the change from baseline to final value in the total UNS Raw score.

## 4.5.3.1.1 Primary analysis

Analysis:

In order to meet the primary objective of the study, the superiority of Pitolisant (BF2.649) as compared to placebo on efficacy after a 7-week treatment period will be assessed, from the UNS total score expressed in terms of change from baseline to Final value. After a Multiple Imputation, the main inferential model with the center as random effect described in section 4.1.3.1 will be used. The assumptions underlying the model will be checked.

The difference between treatment groups will be calculated as BF2.649 minus placebo. Thus, considering the main analysis, a negative treatment difference will be in favour of BF2.649.

The ICH-E9(R1) addendum on Estimands and Sensitivity Analysis in Clinical Trials (ICH, 2020) provides a framework for defining an estimand which is characterized by five attributes: population, endpoint, intercurrent events and population-level summary. The primary estimand for the primary endpoint of the study is defined with mixed strategies for intercurrent events and described in this table (based on the estimand terminology).

The following table summarizes the main endpoint according to the Estimand Notation (ICH-E9R1):

Attribute 	Primary definition		Rationale (as needed)
Population	Intended to include narcoleptic children from 6 to less than 18 years of age with/without cataplexy.		
Endpoint	Ullanlinna Narcolepsy Scale (UNS) at V6, V7		
		•	
Intercurrent events	Event	Strategy	Rationale (as needed)
	Receipt of assigned study treatment	Treatment policy	Strategy applied to align the estimand with the application of the ITT principle.
	Prohibited concomitant medication during the study treatment period	While on treatment	Strategy applied to assess the treatment effect up to the last observation at or prior to the time of the prohibited concomitant medication, which marks the end of adherence to treatment.
	Premature discontinuation from the study at any time	Hypothetical strategy	Strategy applied to estimate what the treatment effect would have been if patients adhered to the treatment by assuming that missing data arise from a missing at random (MAR) mechanism.
Population	Difference in LS means from ANCOVA model		
summary	between treatment groups.		

## Statistical elements:

For this comparison the following elements will be provided in a summary table:

- Estimate (standard error) of the difference between adjusted treatment group means.
- Two-sided 95% CI of the estimate.
- p-value (to be compared to 0.05).

## 4.5.3.1.2 Sensitivity and other analyses

Sensitivity analyses will be performed to assess the robustness of the primary analysis results:

- Using MNAR option of the MI imputation (removing the treatment effect in the imputation model of the partially-complete data sets).
- Using the same model as for the primary analysis will be performed with the center as fixed effect instead of random effect.
- Using the same model as for the primary analysis will be performed with in addition the oxybate sodium intake and treatment-by- oxybate sodium intake interaction as fixed effects.
- Using an observed Cases analysis: The same model as for the primary analysis will be performed in patients having a value of UNS total score at V6 or V7 (i.e. in this case analysis restricted to completers the double blind period).
- Using the same model as for the primary analysis will be performed by actual treatment group, only if actual group is different from randomized group.

The same statistical elements to estimate the treatment effect as for primary analysis will be provided.

In addition, value and change from baseline descriptive statistics at each visit by treatment group will be provided, overall and by subgroups.

